Pre-intervention assessment will include pain intensity/evaluation using point system and quality of life measured by the neck disability index.

Post-intervention assessment will include pain intensity/evaluation using point system, administered immediately after the intervention, and one week following the intervention using phone survey or online survey depending on patient preference and comfort.

Intervention

Group1 (PCOM): Will receive the muscle energy technique; trigger point isolated followed by post isometric relaxation muscle energy technique

Group 2 (AtlantiCare Regional Medical Center): Will receive lidocaine injection technique

Outcome Measures

1. *Pain intensity*; measured using a point system; where 0 = no pain and 10 = maximum pain. Although this is a subjective measurement by the patient, we are interested in looking at the difference between pre- and post-intervention pain intensity ratings.
2. *Quality of Life*; measured by the Neck disability Index²² which is used to evaluate neck and upper extremity function. The total score is divided by number of answered questions, subtracted 1 and multiplied by 25, in a scale score that range from 0 to 100, with higher scale scores indicating more disability.

Neck Disability Index score rating²³:

- 0-4 points (0-8%) : no disability,
- 5-14 points (10 – 28%) : mild disability,
- 15-24 points (30-48%) : moderate disability,
- 25-34 points (50- 64%) : severe disability,
- 35-50 points (70-100%) : complete disability

Procedure

Patients that consent to the study and are eligible following the inclusion & exclusion criteria will be recruited into the study. They will fill out the pre-intervention survey in the room. Once the survey is completed, the patient will be placed in a seated position and using palpation, the examiner will identify

the MTrP according to the criteria set by Simons et al. Following the subjective pre-assessment, the intervention will be performed.

Group 1 will be primarily focused on patients from the OMM clinic at PCOM. Patients will be administered muscle energy technique of post isometric relaxation as per the Atlas of Osteopathic Techniques on the symptomatic upper trapezius without treatment of surrounding structures by the osteopathic attending physician.

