- 1 active/latent MTP in the upper trapezius region

The diagnostic criteria to establish myofascial trigger point is adopted from Travell and Simons³ and include:

1. Presence of palpable taut band in the skeletal muscle
2. Presence of hypersensitive tender spot in the taut band
3. Presence of local twitch response upon stimulation of the taut band
4. Reproduction of referred pain upon palpation
5. Presence of spontaneous referred pain pattern

Exclusion criteria: Subjects that exhibited any of the following criteria were excluded from the study:

- Pregnancy or immunocompromise
- Fever/infection
- Previous history of whiplash injury
- Previous history of cervical surgery, cervical radiculopathy, or myelopathy
- Severe disc or cervical lesion
- Evidence of cognitive deficit
- Degenerative or inflammatory disease of the cervical spine or shoulder, fibromyalgia, or neuromuscular diseases
- Use of medications (anticoagulants, anti-inflammatory etc.) or illicit drug use (1 week prior to treatment or follow up)
- Received treatment for MPS a month before the study recruitment

All eligible participants were screened at their respective clinic with the above criteria. Subjects who agreed to participate in the study provided informed consent. At this time, they were given a demographic survey and pre-intervention survey. This survey included a standard pain intensity evaluation using a 0-10 pain scale and a quality-of-life assessment measured by the neck disability index. After enrollment and pre-intervention assessment, the appropriate intervention was administered to

the patient; patients at the Philadelphia OMM clinic received muscle energy treatment, while patients at the Atlanticare Pain Management clinic received lidocaine with dry needling.

Participants presenting to the PCOM OMM clinic were treated with the muscle energy technique of post isometric relaxation on the symptomatic upper trapezius by a board-certified osteopathic physician. After placing patient in a supine position, the shoulder on the affected side was stabilized with one arm. Using the other arm, the head was sidebent contralaterally and rotated ipsilaterally until the restriction barrier was encountered. This position was then maintained for 10 seconds while a normal respiratory rhythm was maintained. After 10 seconds the position was extended further into the barrier and held for 30 seconds and process repeated.

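### The Protocol's Neck Disability Index conversion does not fit the 0 to 50 point bands printed below it, and one band limit is misprinted (64% for 68%)

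*Protocol*

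**What the plan says.** In the Protocol, Outcome Measures item 2 makes the NDI the measure of quality of life. The conversion is: "The total score is divided by number of answered questions, subtracted 1 and multiplied by 25, in a scale score that range from 0 to" (maximum 100). Higher scores mean more disability.

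The rating list that follows gives each band in points, with a percentage in brackets:

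- "0-4 points (0-8%) : no disability"
- "5-14 points (10 – 28%) : mild disability"
- "15-24 points (30-48%) : moderate disability"
- "25-34 points (50- 64%) : severe disability"
- a top band of 35 to 50 points, or 70 to 100%.

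The Protocol does not give the number of items or how each item is coded. It also does not say whether a patient is banded from raw points or from the converted score.

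The SAP (Study Design) says that the pre-intervention survey included "a quality-of-life assessment measured by the neck disability index". It gives no scoring rule. Its Outcome Measures section lists pain intensity only, and its Results and tables contain no NDI value.

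**The concern.** The formula takes the mean item score, subtracts 1 and multiplies by 25. It runs from 0 to 100 only when the lowest item score is 1 and the highest is 5. The bands start at 0 points, which requires items that can score 0. The formula and the bands therefore cannot both describe the same form.

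Quality of life is in the Protocol's title and primary aim, and its Data Analysis section plans a formal analysis of it. The NDI is the only measure of it, and this paragraph is the only scoring instruction in either document. Scored as written on a 0 to 50 form, low totals become negative. NDI levels, differences and SDs would be on a different scale from the printed percentages. A reader who compares the converted score with those percentages would place some patients in too low a band.

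**Working it through.** **Inputs.** All are from Protocol, Outcome Measures item 2: the formula, the stated range of 0 to 100, and the five bands. Assumption: 10 items coded 0 to 5, because the point scale ends at 50.

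**1. Percentages in the bands.** Twice the points gives 0, 8, 10, 28, 30, 48, 50, 68, 70 and 100 for 0, 4, 5, 14, 15, 24, 25, 34, 35 and 50 points. Every printed limit is reproduced except one: 34 points is printed as 64%, not 68%. As printed, totals of 33 and 34 (66% and 68%) fall in no percentage band.

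**2. Stated range.** For total T and n answered items, the score is (T/n - 1) x 25.

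- T = 0: (0 - 1) x 25 = -25 for any n. This needs no assumption about the number of items.
- T = 50: the score is 100 only if n = 10, since (50/10 - 1) x 25 = 100. With n = 9 it is 113.9 and with n = 11 it is 88.6.

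The stated range of 0 to 100 is therefore not reproduced on the 0 to 50 scale. It is -25 to 100.

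**3. Size, with n = 10.** The score is 2.5T - 25, the bands imply 2T, and the shortfall is 25 - 0.5T.

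| Points T | Band by points | 2T (%) | 2.5T - 25 | Shortfall | Band if the score is read against the percentages |
|---|---|---|---|---|---|
| 0 | none | 0 | -25 | 25 | outside all bands |
| 10 | mild | 20 | 0 | 20 | none |
| 15 | moderate | 30 | 12.5 | 17.5 | mild |
| 25 | severe | 50 | 37.5 | 12.5 | moderate |
| 35 | complete | 70 | 62.5 | 7.5 | severe |
| 50 | complete | 100 | 100 | 0 | complete |

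Over the 51 possible totals, with the severe limit read as 68%:

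- 10 totals (0 to 9) are negative and fit no band.
- 19 totals (10 to 13, 15 to 21, 25 to 29, 35 to 37) drop exactly one band.
- 22 totals (14, 22 to 24, 30 to 34, 38 to 50) keep their band.
- Only T = 50 gives the same value both ways.

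With the limit left at 64%, two of the 19 (totals 36 and 37, scores 65 and 67.5) fall between bands.

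**4. Effect on tests.** Let m be the mean of the answered items. The Protocol score is 25m - 25. The percentage on 0 to 5 coding is 20m. So the Protocol score is 1.25 x percentage - 25 for every patient, including those with unanswered items. Differences and SDs both grow by 1.25, so t, F, p and standardized effects do not change.

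**5. Other codings, 10 items.**

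| Item coding | Total | Formula score |
|---|---|---|
| 0 to 4 | 0 to 40 | -25 to 75 |
| 0 to 5 | 0 to 50 | -25 to 100 |
| 1 to 5 | 10 to 50 | 0 to 100 |
| 1 to 6 | 10 to 60 | 0 to 125 |

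Coding 1 to 5 makes the formula correct. Totals then start at 10, so the no-disability band and mild totals of 5 to 9 cannot occur. No coding tried fits both the formula's range and the bands.

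**The case against.** The strongest reply is that little depends on the formula. The bands are given in raw points first, so a patient can be classified without converting anything, and the Protocol never says to read the converted score against the percentages. The SAP lists only pain as an outcome and reports no NDI value. The documents also do not settle which part is wrong, because with items coded 1 to 5 the formula is sound and the bands fail.

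All of this stands, and it limits the point. It does not remove the contradiction: under any coding tried, either the formula or the bands must change.

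A reader might go further and infer that every quality-of-life score is wrong, or that the comparison of a milder OMM group (baseline pain 2.76) with a more severe lidocaine group (baseline pain 7) is distorted. The documents support neither. A total of 50 converts correctly, 22 of 51 totals keep their band, and no score is shown to have been computed this way. The shortfall is larger at low totals only because the error is linear, and a linear rescaling leaves every group test unchanged. Baseline pain also cannot stand in for NDI values that are not given.

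**Conclusion.** The Protocol's scoring rule is wrong as written. That a zero total converts to -25 follows from the printed text alone. So does the 64% misprint, on the list's own rule of twice the points.

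The rest of the size depends on 10 items coded 0 to 5: a range of -25 to 100, 10 negative totals, 19 totals one band too low if read against the percentages, and differences and SDs 1.25 times too large. What would change is NDI levels and anything expressed in NDI units. Hypothesis tests and banding from raw points would not change.

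This is a fault in the specification. Nothing shows that the baseline forms were scored with this formula. A separate gap is that the Protocol lists the NDI before the intervention only, while its Data Analysis section plans a three-time-point analysis of quality of life.

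**What to change.** 1. State the number of items and the item coding of the form that was used.
2. If items are coded 0 to 5, replace the formula with NDI % = total points / (5 x answered items) x 100. If they are coded 1 to 5, keep the formula and replace the bands with ones that match it.
3. If the 0 to 50 point bands stay, correct the upper limit of the severe band from 64% to 68%.
4. Say whether patients are banded from raw points or from the converted score.
5. Before reporting any baseline NDI value, check which formula produced it. If items are coded 0 to 5 and the printed formula was used, rescore with percentage = (score + 25) / 1.25. For example, (12.5 + 25) / 1.25 = 30, which matches 15 points.

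The cost is small: a sentence or two and one number in the Protocol (or a replaced band list under 1 to 5 coding), plus at most one recomputed column. No new data are needed.

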Group 2 will be comprised of patients from AtlantiCare Regional Medical Center pain clinic and will be administered trigger point dry needling and lidocaine injection. The treatment will be administered by the pain clinic attending physician. After application of a coolant to numb the area, the isolated trigger point will be penetrated using a 30-gauge needle, to a depth adjusted depending on the patient, into the subcutaneous tissue. The patient will be warned about possible unpleasant sensations and mild pain associated with contraction of the tight band of muscle. Multiple needle insertions will be attempted to achieve MTrP inactivation, with the needle being withdrawn to the subcutaneous layer but not from the skin during each insertion, approximately lasting for 1-2 minutes ^{26,27}. Once the fascial tension is relieved, 0.5% lidocaine will be injected, and the needle will be withdrawn from the skin. The procedure will be terminated with hemostasis achieved.

Once the intervention is completed, the patient will be asked about the reduction in pain following the intervention and administered the post intervention survey. A week after the intervention, they will be called/mailed to ask about their pain intensity using the same post intervention survey by the medical students.

Safety Management:

Patients are free to withdraw from the study at any time should they choose to. Since the study procedures are not greater than minimal risk, adverse events are not expected. If any serious adverse effects or unaccounted events may occur, they will be reported to the IRB and patients will be discontinued from the study. The data from withdrawn patients will not contribute to the study statistics.

Data Analysis

The data will be analyzed using SPSS version 27.0 for Windows (IBM Corp. Released 2020. IBM SPSS Statistics for Windows, Version 27.0. Armonk, NY: IBM Corp). Values of interest include measures of central tendency, i.e. mean, standard deviation, normal distribution, confidence intervals etc. To be considered a statistically significant finding, the alpha level will be set at 0.05. A descriptive analyses of the outcome variables will be conducted to compare between the intervention groups. The homogeneity of sociodemographic data (age, sex, comorbid conditions) and treatment groups will be analyzed using the Fischer test and Pearson chi square test, respectively.

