Participants presenting to the Atlanticare Pain Management clinic received a lidocaine injection after dry needling into the location of the MTP by a board-certified pain management physician. First, the upper trapezius MTP was identified and isolated. After application of a coolant to numb the area, the isolated trigger point was penetrated using a 30-gauge needle, to a depth adjusted depending on the patient, into the subcutaneous tissue. The duration of treatment was approximately 1-2 minutes. Once the myofascial tension was relieved, 2 mL of 0.5% lidocaine was injected into the MTP.

After their respective interventions, the patient completed an immediate post-intervention survey, consisting of a 0-10 pain scale. Finally, approximately 7-10 days after the intervention, patients were contacted by telephone to complete the one-week post-intervention survey consisting of a 0-10 pain scale.

Outcome Measures

Pain intensity; measured using a point system; where 0 = no pain and 10 = maximum pain. Although this is a subjective measurement by the patient, we are interested in looking at the difference between pre- and post-intervention pain intensity ratings.

Data Analysis

The data was analyzed using R software. Values of interest include mean, median, standard deviation, normal distribution, confidence intervals etc. Intergroup and intra-group comparisons were conducted using independent t-tests and paired t-tests, respectively. Alpha level is set at 0.05 and p values less than that will be considered statistically significant. A descriptive analysis of the outcome variables was conducted to compare between the intervention groups. The homogeneity of sociodemographic data (age, sex, comorbid conditions) and outcome measures were analyzed using the Fischer test and Pearson chi square test, respectively.

The outcome measures were analyzed separately in both treatment groups. The contrast between the treatment groups was analyzed. A univariate analysis of the difference of the outcome variables at the different time points (before the intervention, immediately after the intervention, and a week post the intervention) were obtained through the student *t*-tests. A multivariate analysis was carried out using multiple logistic regression models with age, sex, and intervention group (Injection = 0, OMM = 1) factored as the independent variables.

Results

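### Serious events must go to the IRB, but neither post-treatment survey asks about adverse events and the SAP results do not mention harms

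*Protocol*

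**What the plan says.** The protocol's Safety Management section gives its expectation first: "Since the study procedures are not greater than minimal risk, adverse events are not expected". The reporting duty follows: "If any serious adverse effects or unaccounted events may occur, they will be reported to the IRB and patients will be discontinued from the study". That paragraph also leaves the data of withdrawn patients out of the statistics.

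The Study Design section fixes what is collected after treatment: "Post-intervention assessment will include pain intensity/evaluation using point system, administered immediately after the intervention, and one week following the intervention". The Procedure section describes the only planned contact after the visit, made a week later by medical students: "they will be called/mailed to ask about their pain intensity using the same post intervention survey". Study Administration makes the pre- and post-intervention surveys the primary data records.

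The SAP's Study Design section describes the immediate survey as a 0-10 pain scale and says of the later contact that "patients were contacted by telephone to complete the one-week post-intervention survey consisting of a 0-10 pain scale". Its Results section and Tables 1 and 2 contain no statement about adverse events.

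**The concern.** The plan sets a duty to report certain events but no step that would bring them to light. The surveys ask about pain, and the surveys are the data. Neither document defines an adverse event or gives a form, an observation period, a person responsible for collecting events, or a safety table.

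Two things are at stake. For patients, a problem that starts at home reaches the investigators only if the patient raises it unasked. For readers, a comparison of a needle procedure with a manual technique appears without a word on harms, and silence cannot be told apart from a count of zero.

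**Working it through.** The documents state no adverse event rate, safety sample size or detection probability, so there is no figure to reproduce. The check sets the safety text beside the data collection text, contact by contact.

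1. **During treatment.** In both groups an attending physician gives the treatment. For the injection group the Procedure section says "The treatment will be administered by the pain clinic attending physician". An event at this stage could be seen, but no form or field for recording it is named.

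2. **Immediate survey.** Under the protocol's Procedure section the patient is asked how far pain has fallen and then completes the post-intervention survey. The assessment text in the protocol and the SAP's Study Design section both give its content as a pain score. Adverse event items: 0.

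3. **One-week survey.** The protocol repeats the same survey by phone or remotely, administered by medical students. The SAP describes a telephone contact at about 7 to 10 days with a 0-10 pain scale. Adverse event items: 0.

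4. **Total.** Surveys with an adverse event item: 0 + 0 = 0 of 2.

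5. **Could quality of life fill the gap?** The protocol's Data Analysis section plans a three-time-point analysis for each dependent variable, which implies a Neck Disability Index after treatment. The assessment text collects that index only before treatment. These passages need reconciling, but the index measures disability and would not record adverse events either way.

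6. **Could a detected event disappear?** Safety Management discontinues patients with serious or unaccounted events and separately excludes withdrawn patients' data. If discontinued patients count as withdrawn, which the text does not settle, such a patient leaves the study statistics. The IRB report would remain, but the results would not show the event.

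7. **What the results show.** The SAP reports 10 lidocaine and 21 OMM patients, 10 + 21 = 31 in all. One lidocaine patient was lost by one week and excluded, leaving 9 + 21 = 30, as in Table 2. No reason for the loss is given. Nothing suggests harm, but the data collected could not show whether there was any.

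**The case against.** The strongest reply is that this is a small cohort of patients managed under usual care. A physician is present at treatment, the needling procedure ends only once bleeding is controlled, and patients are questioned straight afterwards. A later problem can be mentioned at the one-week contact or to the clinic. The consent form was not available for this review and may tell patients to report problems. All of this stands. It limits the gap to active elicitation, chiefly after the patient leaves. It does not close it, because every route after the visit depends on the patient speaking up unasked.

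A reader might also infer four stronger things that the documents do not support:

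- **That serious events cannot be detected at all.** Physician observation and spontaneous reports remain possible.
- **That the protocol contradicts itself.** It says "The patient will be warned about possible unpleasant sensations and mild pain", but the sentence ties this to contraction of the tight muscle band. Warning of a mild, foreseen sensation is compatible with a minimal-risk judgement, and the next sentence of Safety Management provides for serious events.
- **That the SAP claims better tolerability for OMT.** Its Discussion calls OMT non-invasive and low cost and rests the case on comparable efficacy. It does not compare harms.
- **That a zero-event bound measures the defect.** For 10 lidocaine patients the exact one-sided 95% upper limit with no events is 1 - 0.05^(1/10) = 0.259. That figure reflects the group size and assumes every patient was asked. Adding the question would not change it, and without the question no such bound applies.

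**Conclusion.** The point holds as a gap in planned ascertainment and reporting. As described, 0 of 2 post-treatment surveys elicit adverse events, the reporting rule has no planned collection step behind it once the patient leaves, and the SAP's Results make no harms statement. How many events were missed, if any, cannot be estimated from the documents.

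The conclusion assumes that the surveys contained only what the two documents describe. The further risk that a detected event drops out of the results assumes that discontinued patients are treated as withdrawn. The point does not affect the pain analysis. It is worth acting on because the remedy is cheap and serves patient safety.

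**What to change.** For any continuation, or for the larger trials that the SAP's Discussion anticipates:

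- Add one open question about problems since treatment to the immediate and one-week surveys, worded identically in both groups.
- Route any positive answer to the existing site investigator. This matters because the protocol has medical students make the one-week contact.
- Tabulate events by group for all treated patients, including those discontinued or withdrawn, and print the table even when the counts are zero. The exclusion of withdrawn patients' data should be stated not to apply to this table.

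For the completed data the survey change comes too late. The report should state that harms were not systematically elicited, so the comparison covers pain only.

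The cost is one extra item on two existing surveys, one small table, one sentence in the report and a little review time. No added visit is needed.

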The study is a prospective cohort study comprised of participants between ages 25-75 presenting to Atlanticare Regional Medical Center interventional pain department and Philadelphia College of Osteopathic Medicine OMM Clinic between April 2021 and May 2021 with trigger point in the upper trapezius muscle. It is expected that approximately 60 patients will be enrolled to produce approximately 50 evaluable subjects.

Inclusion Criteria: The subjects will only be recruited into the study if they have met all the following criteria:

- Ages between 25 and 60 years.
- Previous or current diagnosis of MTrP in the upper trapezius region according to the criteria set by Simons et al.³
- 1 active/latent MTrP in the upper trapezius region

The diagnostic criteria to establish myofascial trigger point is adopted from Travell and Simons³ and include:

1. Presence of palpable taut band in the skeletal muscle
2. Presence of hypersensitive tender spot in the taut band
3. Presence of local twitch response upon stimulation of the taut band
4. Reproduction of referred pain upon palpation
5. Presence of spontaneous referred pain pattern

Exclusion criteria: Any subject that exhibits any of the following criteria will be excluded from the study:

- Pregnancy or immunocompromise
- Fever/infection
- Previous history of whiplash injury
- Previous history of cervical surgery, cervical radiculopathy, or myelopathy
- Severe disc or cervical lesion
- Evidence of cognitive deficit
- Degenerative or inflammatory disease of the cervical spine or shoulder, fibromyalgia, or neuromuscular diseases
- Use of medications (anticoagulants, anti-inflammatory etc.) or illicit drug use (1 week prior to treatment or follow up)
- Received treatment for MPS a month before the study recruitment

All the patients of interest that present to AtlantiCare Regional Medical Center pain clinic and Philadelphia College of Osteopathic Medicine OMM Clinic that meet the relevant inclusion and exclusion criteria will be invited to participate in this study. The subjects will be informed of the purpose of the study and asked for informed consent. If recruited into the study, they will be administered a pre-intervention survey. Subjects will then be managed according to standard of care by their point of care physician. Following the intervention they will be administered a post-intervention survey immediately following the intervention and one-week post.

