The study was completed at two primary locations. There were a total of 10 eligible participants from the lidocaine treatment group and 21 eligible participants from the OMM treatment group enrolled after screening for the inclusion and exclusion criteria. 1 subject from the lidocaine treatment group was lost during follow-up at one week post intervention and thus excluded from the per protocol analysis of the study. The remaining participants' data were analyzed in SPSS 26. No significant difference was found between the two groups in regard to sociodemographic data (Table 1). At baseline, the OMM group had a mean pain intensity level of 2.76 (SD 1.8) while the lidocaine treatment group had a mean pain intensity level of 7 (SD 2.8). Descriptive statistics of pain intensity between the two groups demonstrate considerable variance (Table 2).

Within the OMM group, an independent samples t-test found a statistically significant difference between the pre-intervention and immediate post-intervention pain levels, $t(20) = 2.10, p = .048$. The mean pre-intervention pain level ($M = 2.76, SD = 1.84$) was significantly higher than the immediate post intervention pain level ($M = 1.86, SD = 0.96$). An independent samples t-test found a statistically significant difference between pre-intervention and one-week post-intervention pain levels, $t(20) = 2.68 p = .014$. The mean pre-intervention level of pain ($M = 2.76, SD = 1.84$) was significantly higher than one-week post-intervention ($M = 1.81, SD = 2.01$).

Within the lidocaine group, an independent samples t-test did not demonstrate a statistically significant difference between pre-intervention and immediate post-intervention pain levels, $t(20) = 1.17, p = 0.27$. The mean pain level pre-intervention ($M = 7, SD = 2.87$) was higher than immediately post-intervention ($M = 6.60, SD = 2.32$). When evaluating the difference in level of pain from pre-intervention to one-week post-intervention, an independent samples t-test was not statistically significant, $t(20) = 2.16 p = .062$. The mean level of pain pre-intervention ($M = 7, SD = 2.87$) was higher than one-week post-intervention ($M = 4, SD = 2.18$). Pain intensity between the two groups are also demonstrated graphically in Figure 1, with time point one corresponding to pre-intervention, two corresponding to immediately post-intervention and three corresponding to 1 week post intervention.

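### The protocol excludes all data of withdrawn patients from the statistics, and the SAP's mixed ANOVA separately drops two observed ratings of one of the 10 lidocaine patients, with no analysis of everyone enrolled

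*Protocol*

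**What the plan says.** **Protocol, Safety Management.** Three statements stand together. On voluntary withdrawal: "Patients are free to withdraw from the study at any time should they choose to". On harms: "If any serious adverse effects or unaccounted events may occur, they will be reported to the IRB and patients will be discontinued from the study". Then the data rule: "The data from withdrawn patients will not contribute to the study statistics". The protocol does not say whether a discontinued patient counts as a withdrawn one.

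**Protocol, Study Design.** "It is expected that approximately 60 patients will be enrolled to produce approximately 50 evaluable subjects". Some loss was therefore expected, but Data Analysis gives no method for incomplete patients.

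**SAP, Results.** "There were a total of 10 eligible participants from the lidocaine treatment group and 21 eligible participants from the OMM treatment group enrolled". One lidocaine patient was "lost during follow-up at one week post intervention and thus excluded from the per protocol analysis of the study". The SAP reports no withdrawal and no serious adverse effect. It does not cite the protocol's data rule, and it defines no analysis set other than the per-protocol one.

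**SAP, Tables 1 and 2.** Table 1 shows 10 lidocaine patients. Table 2, which matches the mixed ANOVA, shows 9 at every time point.

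**The concern.** The data rule is a stated instruction, not a silence. A patient who gives a baseline and an immediate rating and then leaves contributes neither. Leaving happens after treatment and may depend on how treatment went, so the rule can select on outcome. Its natural reading also takes in patients discontinued for serious adverse effects, because it follows directly on that sentence and nothing else says what happens to their data. Groups are set by clinic and not by randomisation, so a selective loss in one of them adds to a comparison that is already fragile.

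The ANOVA raises a related but separate problem. A design that needs all three ratings from every patient discards partial records, and here the only partial record is in the smaller arm. With 9 or 10 patients, one score can decide which side of 0.05 a test falls on, and the SAP does not show how far its one-week result depends on that score.

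**Working it through.** **1. The plan's own counts.** 10 + 21 = 31 enrolled; 31 − 1 = 30 analysed, as in Table 2. The Table 2 totals reproduce:
- baseline (21 × 2.76 + 9 × 7.00)/30 = 4.03
- immediate (21 × 1.86 + 9 × 6.56)/30 = 3.27
- one week (21 × 1.81 + 9 × 4.00)/30 = 2.47

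The printed interaction denominator of 56 equals (30 − 2) × 2, so the ANOVA used 30 patients. With the Greenhouse-Geisser correction the denominator is 56 × 1.65/2 = 46.2, and F = 3.90 on (1.65, 46.2) df gives p = 0.034, as stated.

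The planned loss is (60 − 50)/60 = 16.7%, or one patient in six. The protocol states no dropout rate, so this is only implied.

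**2. The dropped patient's ratings.** SAP Results gives lidocaine values that fit n = 10 (baseline 7, SD 2.87; immediate 6.60, SD 2.32). Table 2 gives n = 9 (7.00, SD 3.04; 6.56, SD 2.45). The difference in sums is the missing patient:
- baseline: 10 × 7.00 − 9 × 7.00 = 7
- immediate: 10 × 6.60 − 9 × 6.56 = 6.96, so 7 on a whole-number scale

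Check on the SDs, adding a score of 7 to the nine:
- baseline: √[(8 × 3.04² + 0.9 × 0²)/9] = 2.87 (stated 2.87)
- immediate: √[(8 × 2.45² + 0.9 × 0.44²)/9] = 2.31 (stated 2.32)

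The patient went from 7 to 7. The other nine improved by a mean of 7.00 − 6.56 = 0.44. Over all ten the immediate change is 7.00 − 6.60 = 0.40, so dropping the patient moves it by 0.04.

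**3. Where the patient was used.** The printed immediate mean and SD (6.60, 2.32) are those of ten patients. The immediate test agrees: t = 1.17 gives p = 0.272 on 9 df, 0.276 on 8 df and 0.256 on 20 df, against a stated 0.27. The gap between 8 and 9 df is within rounding of t, so it is the mean and SD that settle n = 10. At one week t = 2.16 gives 0.063 on 8 df, 0.059 on 9 df and 0.043 on 20 df, against a stated .062, so n = 9. The same patient is thus in Table 1 and the immediate within-group test, out of the one-week test, and out of the ANOVA at all three times.

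**4. How much the missing score matters.** Let x be the unknown one-week score.
- SD of change for the nine, from t = 2.16: 3.0 × √9/2.16 = 4.17
- one-week mean for ten: (9 × 4.00 + x)/10
- mean reduction: 7.00 minus that mean
- SD of change for ten: √[(8 × 4.17² + 0.9 × (7 − x − 3)²)/9]
- t = reduction × √10/SD, on 9 df

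| x | One-week mean | Reduction | t | p |
|---|---|---|---|---|
| 0 | 3.6 | 3.4 | 2.61 | 0.028 |
| 4 | 4.0 | 3.0 | 2.41 | 0.039 |
| 5 | 4.1 | 2.9 | 2.33 | 0.045 |
| 6 | 4.2 | 2.8 | 2.23 | 0.053 |
| 7 | 4.3 | 2.7 | 2.11 | 0.064 |
| 10 | 4.6 | 2.4 | 1.74 | 0.116 |

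The stated result (mean 4.00, reduction 3.0, p = .062) lies inside this range. A score of 5 or lower puts p below 0.05; 6 or higher does not. Each row treats x as if it had been observed, which overstates precision, so the table shows dependence on one score and is not an analysis to report.

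Against the OMM reduction of 2.76 − 1.81 = 0.95, the between-group difference in one-week reduction runs from 3.4 − 0.95 = 2.45 to 2.4 − 0.95 = 1.45 (completers 3.0 − 0.95 = 2.05). Its sign does not change. The interaction test cannot be recomputed with this patient included, because that needs the individual ratings.

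**The case against.** The strongest reply is that the two parts are not connected. The SAP patient was lost to follow-up, not withdrawn and not harmed, and a repeated-measures ANOVA drops incomplete cases by construction, so no withdrawal rule is needed to explain the exclusion. This stands: a reader might infer that the SAP was applying the protocol's rule, but it never cites it and it uses the patient's first two ratings elsewhere.

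A reader might also infer that a poor outcome was removed and the lidocaine arm flattered. The documents do not support that. The one-week score is unknown. No immediate change says little when the other nine improved by only 0.44 at that point and most of the lidocaine change came later (6.56 to 4.00). Carrying the 7 forward gives a one-week mean of 4.30, but that is one arbitrary value, and its p (0.064) is almost the stated one. A likelihood-based model would move the one-week mean far less. The patient's baseline equals the mean of the nine, and the immediate mean shifts by 6.60 − 59/9 = 0.044, so with a common regression on earlier ratings the shift is about 0.044 times the slope, under 0.05 for any slope up to 1.

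Two further limits stand. The protocol leaves data out of the statistics and does not erase them; under Study Administration, records are destroyed only 5 years after study completion. And coverage of patients discontinued for serious adverse effects is the natural reading, not an explicit statement.

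Finally, recruitment is over, one disclosed loss among 31 is small beside the baseline gap (2.76 against 7.00), and a new protocol sentence cannot change conduct. The comparison of size is fair. It does not justify leaving out observed ratings, and the analysis can still be rerun.

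**Conclusion.** The concern holds in two separate parts. The protocol's data rule excludes withdrawn patients from all statistics and could remove patients with poor outcomes; no document shows that it did. The SAP's mixed ANOVA discards two observed ratings of 1 of 10 lidocaine patients (10%, against 0% of 21 OMM patients), with no all-enrolled analysis and no sensitivity analysis.

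The direction of any bias is unknown. The effect on the immediate lidocaine change is 0.04 points. At one week, a single unknown score spans 1.0 point in the lidocaine mean and decides whether the within-group test is significant at 0.05. The stated one-week result is therefore less certain than it appears, although its point estimate may barely move under a suitable model.

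This rests on whole-number pain ratings, on the printed means and SDs being rounded correctly, and on a change SD of 4.17 back-calculated from t = 2.16 with n = 9. The SAP calls its within-group tests independent-samples; they are treated here as paired, which the one-week p-value fits.

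**What to change.** **Protocol, Safety Management.** Replace the data-rule sentence with one stating that ratings collected before withdrawal or discontinuation are kept and analysed in the group in which the patient was treated. Naming both terms removes the ambiguity about patients discontinued after a serious adverse effect. This concerns data handling only.

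**SAP, Data Analysis.** Add a sentence making the analysis of all 31 enrolled patients primary, using a likelihood-based repeated-measures model on all observed ratings. Report the n = 30 complete-case ANOVA as a sensitivity analysis, and add a second one that varies the missing one-week score over 0 to 10. State the number of patients beside every test.

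**Cost.** Two sentences and one rerun on data already held. The one-week lidocaine result may have to be stated with less certainty.
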